6.7 Medical History

Data on Medical History will be presented for the Safety Analysis Population. Medical History consists of the following parts:

- Amyotrophic Lateral Sclerosis (ALS) History
- Other Medical History
- Familial Cancer History

ALS History

ALS history consists of following data:

- ALS diagnosis, values are:
 - Clinically definite ALS
 - Clinically probable ALS
 - Clinically probable laboratory-supported ALS
- Site on Onset, values are:
 - Limb
 - Bulbar (includes respiratory)
 - Both limb and bulbar
 - Other
- Experiencing symptoms of lower motor dysfunction
 - Yes
 - No
- Experiencing upper motor neuron symptoms
 - Yes

QMD Ref: Worldwide-TMP-ST-005-7.0 Effective: 12Aug2019	Governing QMD: Worldwide-SOP-ST-001
Confidentiality Statement	

This document is the property of Worldwide Clinical Trials Inc. and may not be duplicated, copied, altered or removed from company without prior approval from Worldwide Quality Assurance or in compliance with Worldwide Standard Operating Procedures.

Worldwide Clinical Trials Controlled Quality Management Document			
 WORLDWIDE CLINICAL TRIALS	Sponsor:	Helixmith Co., Ltd.	
	Protocol Number:	VMALS-002-2	
STATISTICAL ANALYSIS PLAN VERSION 3.0			

- No

Other Medical History

Other Medical History consists of previous (Ongoing=No) and ongoing (Ongoing=Yes) conditions. Previous and ongoing conditions at screening will be presented separately. Conditions will be coded by Medical Dictionary of Regulated Activities (MedDRA, version 23.0, or later) primary system organ class (SOC) and preferred term (PT).

Familial Cancer History

Familial Cancer History consists of:

- Existence of cancer in the nearest relatives
 - Yes
 - No
- Description of cancer and relationship to a participant
 - Mother
 - Father
 - Sister
 - Brother
 - Maternal grandmother
 - Maternal grandfather
 - Paternal grandmother
 - Paternal grandfather
 - Aunt
 - Uncle
 - Other.

All data on Medical History will be presented in tables (Tables 14.1.3.1 – 14.1.3.4) and listings (Listings 16.2.4.5 – 16.2.4.7).

6.8 Prior and Concomitant Medications

Prior and concomitant medications will be presented for the Safety Analysis Population.

Prior and concomitant medications will be coded using WHO Drug dictionary version March 2020 (or later) and summarized using Anatomic Therapeutic Chemical (ATC) Level 3 and Preferred Term.

QMD Ref: Worldwide-TMP-ST-005-7.0 Effective: 12Aug2019	Governing QMD: Worldwide-SOP-ST-001
Confidentiality Statement	

This document is the property of Worldwide Clinical Trials Inc. and may not be duplicated, copied, altered or removed from company without prior approval from Worldwide Quality Assurance or in compliance with Worldwide Standard Operating Procedures.

Worldwide Clinical Trials Controlled Quality Management Document		
 WORLDWIDE CLINICAL TRIALS	Sponsor:	Helixmith Co., Ltd.
	Protocol Number:	VMALS-002-2
STATISTICAL ANALYSIS PLAN VERSION 3.0		

Separate tabulations will be produced for prior and concomitant medications presented by randomized treatment group. Prior medications are defined as all medications starting before the date of first dose of study drug. Concomitant medications are defined as medications taken on or after the date of first dose of study drug. Medications that started before the date of first dose of study drug and continuing after first dose of study drug will be counted in both categories.

All data on prior and concomitant medications will be presented in tables (Tables 14.3.8.1 and 14.3.8.2) and listings (Listings 16.2.4.8 and 16.2.4.9).

6.9 Exposure to Study Drug

Exposure to study drug will be presented for the Safety Analysis Population.

Number of performed injections and amount of performed injections by anatomic target area, side and total for each dosing day, each treatment cycle and for whole study will be presented by treatment group (Tables 14.3.5.1 and 14.3.5.2). Administered volume of Engensis will be presented in the same manner for Engensis group (Table 14.3.5.3).

All data on exposure will be presented in listings (Listings 16.2.10.1 and 16.2.10.2).

6.10 Treatment Compliance

Treatment compliance will be presented for the Safety Analysis Population.

Descriptive statistics for each side separately and total at each treatment day and treatment cycle as well as for whole study, as described in Section 6.2.9, will be presented by treatment group (Table 14.3.5.4).

Values of treatment compliance will be presented in listing (Listing 16.2.10.3).

6.11 Efficacy Analyses

Not applicable in this SAP.

6.12 Pharmacokinetic Analyses

Not applicable in this SAP.

6.13 Pharmacodynamic Analyses

Not applicable in this SAP.

6.14 Safety Analyses

QMD Ref: Worldwide-TMP-ST-005-7.0 Effective: 12Aug2019	Governing QMD: Worldwide-SOP-ST-001
Confidentiality Statement	

This document is the property of Worldwide Clinical Trials Inc. and may not be duplicated, copied, altered or removed from company without prior approval from Worldwide Quality Assurance or in compliance with Worldwide Standard Operating Procedures.

Worldwide Clinical Trials Controlled Quality Management Document		
 WORLDWIDE CLINICAL TRIALS	Sponsor:	Helixmith Co., Ltd.
	Protocol Number:	VMALS-002-2
STATISTICAL ANALYSIS PLAN VERSION 3.0		

The safety analyses will be presented by the treatment received for the Safety Analysis Population.

6.14.1 Adverse Events

All study-related Adverse Events (AEs) will be collected starting after completion of the informed consent process at Screening to Day 0/randomization. Treatment-Emergent Adverse Events (TEAEs) and Treatment-Emergent Serious Adverse Events (TESAEs) will be collected after first injections on Day 0 through Day 180/End of Treatment or the last Study Visit up until the time that the Participant withdraws consent. All Serious Adverse Events (SAEs) will be collected from the completion of the informed consent process until Study Day 180 or the last Study Visit up until the time that the Participant withdraws consent. Any SAE occurring after consent and before the first injection on Day 0 should be recorded and reported only if associated with a protocol-specified procedure. Any AEs reported during Screening after completion of informed consent will be collected and recorded separately from TEAEs reported on Day 0 and through the end of the study.

Medical occurrences that begin before the start of study intervention and not related to required study procedures, but after obtaining informed consent will be recorded on the Medical History/Current Medical Conditions section of the eCRF and not as AEs.

Adverse events with relationship equal to “Possibly related”, “Probably related” and “Definitely related” will be considered as adverse events related to study medication. If an AE has missing relationship it is assumed to be related to the study drug for analysis purposes.

Adverse events with fatal outcome will be considered as fatal events. Maximum severity will be assumed for an AE with missing severity.

AEs will be coded using Medical Dictionary of Regulated Activities (MedDRA, version 23.0, or later) by System Organ Class (SOC) and preferred term (PT).

Adverse Event (AE) Definition

- An AE is any untoward medical occurrence in a patient or clinical study Participant, temporally associated with the use of study intervention, whether or not considered related to the study intervention.
- NOTE: An AE can therefore be any unfavorable and unintended sign (including an abnormal laboratory finding), symptom, or disease (new or exacerbated) temporally associated with the use of study intervention.

Treatment-Emergent Adverse Event (TEAE) Definition

QMD Ref: Worldwide-TMP-ST-005-7.0 Effective: 12Aug2019	Governing QMD: Worldwide-SOP-ST-001
Confidentiality Statement	

This document is the property of Worldwide Clinical Trials Inc. and may not be duplicated, copied, altered or removed from company without prior approval from Worldwide Quality Assurance or in compliance with Worldwide Standard Operating Procedures.

Worldwide Clinical Trials Controlled Quality Management Document			
 WORLDWIDE CLINICAL TRIALS	Sponsor:	Helixmith Co., Ltd.	
	Protocol Number:	VMALS-002-2	
STATISTICAL ANALYSIS PLAN VERSION 3.0			

- An event that emerges during treatment, having been absent at pretreatment, or worsens relative to the pretreatment state, as defined in the E9 Guidance. AE will be considered as TEAE if it emerged or worsened on the day of first dosing or later to the end of study.
- The TEAE is not related to causality / drug relatedness. It may or may not be related to the drug but is considered a TEAE due to its appearance at or after the treatment has been administered.

Serious Adverse Event (SAE) Definition

An SAE is defined as any AE that, at any dose:

a Results in death

b Is life-threatening

The term “life-threatening” in the definition of “serious” refers to an event in which the Participant was at risk of death at the time of the event. It does not refer to an event, which hypothetically might have caused death, if it were more severe.

c Requires inpatient hospitalization or prolongation of existing hospitalization

- In general, hospitalization signifies that the Participant has been detained (usually involving at least an overnight stay) at the hospital or emergency ward for observation and/or treatment that would not have been appropriate in the physician’s office or outpatient setting. Complications that occur during hospitalization are AEs. If a complication prolongs hospitalization or fulfills any other serious criteria, the event is serious. When in doubt as to whether “hospitalization” occurred or was necessary, the AE should be considered serious.
- Hospitalization for elective treatment of a pre-existing condition that did not worsen from

d Results in persistent disability/incapacity

- The term “disability” means a substantial disruption of a person’s ability to conduct normal life functions.
- This definition is not intended to include experiences of relatively minor medical significance such as uncomplicated headache, nausea, vomiting, diarrhea, influenza, and accidental trauma (e.g., sprained ankle), which may interfere with or prevent everyday life functions but do not constitute a substantial disruption.

QMD Ref: Worldwide-TMP-ST-005-7.0 Effective: 12Aug2019	Governing QMD: Worldwide-SOP-ST-001
Confidentiality Statement	

This document is the property of Worldwide Clinical Trials Inc. and may not be duplicated, copied, altered or removed from company without prior approval from Worldwide Quality Assurance or in compliance with Worldwide Standard Operating Procedures.

Worldwide Clinical Trials Controlled Quality Management Document			
 WORLDWIDE CLINICAL TRIALS	Sponsor:	Helixmith Co., Ltd.	
Protocol Number:			VMALS-002-2
STATISTICAL ANALYSIS PLAN VERSION 3.0			

- e Is a congenital anomaly/birth defect
- f Other situations:
 - Medical or scientific judgment should be exercised in deciding whether SAE reporting is appropriate in other situations such as important medical events that may not be immediately life-threatening or result in death or hospitalization but may jeopardize the Participant or may require medical or surgical intervention to prevent one of the other outcomes listed in the above definition. These events should usually be considered serious.
 - Examples of such events include invasive or malignant cancers; intensive treatment in an emergency room or at home for allergic bronchospasm, blood dyscrasias, or convulsions that do not result in hospitalization; or development of drug dependency or drug abuse.

Treatment-Emergent Serious Adverse Event (TESAE)

- A serious event that emerges during treatment, having been absent at pretreatment, or worsens relative to the pretreatment state, as defined in the EP Guidance.
- The TESAE is not related to causality / drug relatedness. It may or may not be related to the drug but is considered a TESAE due to its appearance at or after the treatment has been administered.

Adverse Events of Special Interests (AESI)

There are 4 main categories of AESIs that will be considered in the study:

1. Related to the angiogenesis potential of Engensis
 - Atherosclerosis
 - Cancer
2. Other medical problems in this patient population
 - Pulmonary Medical Problems
 - Progressive Muscle Weakness
 - Bulbar Disease
3. Injection site reactions
4. COVID-19 infections

The following tables will be presented:

- Summary of TEAE (Table 14.3.1.1)

QMD Ref: Worldwide-TMP-ST-005-7.0 Effective: 12Aug2019	Governing QMD: Worldwide-SOP-ST-001
Confidentiality Statement	

This document is the property of Worldwide Clinical Trials Inc. and may not be duplicated, copied, altered or removed from company without prior approval from Worldwide Quality Assurance or in compliance with Worldwide Standard Operating Procedures.

Worldwide Clinical Trials Controlled Quality Management Document			
 WORLDWIDE CLINICAL TRIALS	Sponsor:	Helixmith Co., Ltd.	
	Protocol Number:	VMALS-002-2	
STATISTICAL ANALYSIS PLAN VERSION 3.0			

- TEAEs organized by SOC and PT (Table 14.3.1.2)
- TESAEs organized by SOC and PT (Table 14.3.1.3)
- TEAEs organized by SOC and PT and Maximum Severity (Table 14.3.1.4)
- TEAEs organized by SOC and PT and Maximum Relationship (Table 14.3.1.5)
- TESAEs organized by SOC and PT and Maximum Severity (Table 14.3.1.6)
- TESAEs organized by SOC and PT and Maximum Relationship (Table 14.3.1.7)
- Incidence Injection site reactions by SOC and PT (Table 14.3.1.8)
- Incidence of clinically significant laboratory values (Table 14.3.1.9)
- AESIs organized by SOC and (Table 14.3.1.10)
- TEAEs leading to study discontinuation by SOC and PT (Table 14.3.1.11)
- TESAEs leading to study discontinuation by SOC and PT (Table 14.3.1.12)
- TEAEs leading to study drug withdrawal by SOC and PT (Table 14.3.1.13)
- TESAEs leading to study drug withdrawal by SOC and PT (Table 14.3.1.14)
- TEAEs related to study medication by SOC and PT (Table 14.3.1.15)
- TESAEs related to study medication by SOC and PT (Table 14.3.1.16)

The following listings will be provided:

- All AEs (Listing 16.2.7.1)
- AESIs (Listing 16.2.7.2)
- TESAEs (Listing 16.2.7.3)
- Injection Site Reactions (Listing 16.2.7.4)
- TEAEs leading to study discontinuation (Listing 16.2.7.5)
- TEAEs related to study medication (Listing 16.2.7.6)
- TESAEs leading to death (Listing 16.2.7.7)

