**FOOTNOTES FOR THE SCHEDULE OF ACTIVITIES**

**Note:** The Schedule of Activities includes activities during Screening and all Study Visits.

**Order of Assessments during Visits (if assessment is to be performed):** AEs/TEAEs, vital signs and weight, ALSFRS-R, HHD, ATLIS, pregnancy test, complete physical exam, SVC, ALSAQ-40, other questionnaires (PGIC and CGIC), blood sample collection for laboratory assessments, and muscle biopsy

- a Day 0 is the Baseline Visit
- b The Day 14 Visit will be scheduled 13-15 days after the Day 0 Visit, the Day 74 Visit will be scheduled 13-15 days after the Day 60 Visit, and the Day 134 Visit will be scheduled 13-15 days after the Day 120 Visit
- c Muscle biopsies will be collected as the last procedure of the Visit. It is collected predose on Day 0.
- d Day 84 muscle biopsy is optional.

**Abbreviations:** AEs = adverse events; AESI = adverse events of special interest; ALSFRS-R = Revised Amyotrophic Lateral Sclerosis Functional Rating Scale; ALSAQ-40 = Amyotrophic Lateral Sclerosis Assessment Questionnaire, 40 questions; ATLIS = accurate test of limb isometric strength; CGIC = Clinical Global Impression of Change; D = day; ET = early termination or withdrawal; HHD = Handheld Dynamometry; PGIC = Patient Global Impression of Change; SVC = Slow Vital Capacity; TEAEs = treatment-emergent adverse events; TESAEs = treatment-emergent serious adverse events

1. **Informed Consent** process is to be completed at Screening prior to conducting any study-specific procedures.
2. **Demographics and Baseline Characteristics** will include age, gender, race, and ethnicity and will be collected at Screening.
3. **Medical History and Familial Cancer History:** A medical history and familial cancer history will be obtained at Screening. The Investigator will confirm the diagnosis of ALS using the revised El Escorial / Airlie House diagnostic criteria. Participants will be confirmed as having clinically definite ALS, clinically probable ALS, or clinically probable laboratory-supported ALS  $\leq 4$  years.

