**16. Revised Amyotrophic Lateral Sclerosis Functional Rating Scale (ALSFRS-R)** will be performed at the Clinical Site at Screening, predose on the Days 0, 60, and 120, and on Days 30, 84, 144, and 180/ET.

**17. Handheld Dynamometry (HHD)** will be measured at the Clinical Site predose on Days 0, 60, and 120, and at Visits on Days 30, 84, 144, and 180/ET.

**18. ATLIS** will be measured (only at sites that have the ATLIS equipment) predose on Days 0, 60, and 120, and at Visits on Days 30, 84, 144, and 180/ET.

**19. Amyotrophic Lateral Sclerosis Assessment Questionnaire, 40 questions (ALSAQ-40)** will be measured predose on Day 0 and at Visits on Days 84 and 180/ET.

**20. Patient Global Impression of Change (PGIC) and Clinical Global Impression of Change (CGIC)** will be conducted at Visits on Days 84 and 180/ET.

**21. Muscle Biopsy:** Biopsies of the gastrocnemius muscle around the injection sites will be collected and stored at Day 0 predose, and Days 84 (optional) and 144 (approximately10 days after the second day of injections of Treatment Cycles 2 and 3).

---

22. **Adverse Events (AEs), Treatment-Emergent Adverse Events (TEAEs), Serious Adverse Events (SAEs) and Treatment-Emergent Serious Adverse Events (TESAEs):** AEs will be recorded after informed consent until the first injections on Day 0. After the start of the 1st Injections on Day 0 through Day 180, AEs will be recorded as treatment-emergent adverse events (TEAEs). Treatment-emergent serious adverse events (TESAEs) occurring after randomization and throughout the study will be recorded. SAEs occurring after the completion of the consent process and before the 1st Injections on Day 0 should be recorded and reported as SAEs only if associated with a protocol-specified procedure. All SAEs, and TESAEs occurring after the time of the 1st Injections through the last Study Visit on Day 180, should be recorded and reported to the Sponsor/designee within 24 hours of awareness of the SAE/TESAE by the Site.

23. **Adverse Events of Special Interest (AESIs):** All AESIs will be continuously monitored throughout the study.

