- If the stop date occurs on or after the start of study drug or the event / concomitant medication is ongoing, and the year is the same as the year of first dosing the start date will be imputed as “01-Jan” of the same year or the date of the first dose of study drug whichever is latest. If the year is different from the year of first dosing “01-Jan” will be used.
- If the stop date occurs before the start of study drug, the start date of the event / concomitant medication will be imputed as the “01-Jan” of the same year.

Partial start date (month and year present, but day missing)

- If the stop date occurs on or after the start of study drug or the event / concomitant medication is ongoing, the start date will be imputed as the first day of the same month and

QMD Ref: Worldwide-TMP-ST-005-7.0 Effective: 12Aug2019	Governing QMD: Worldwide-SOP-ST-001
Confidentiality Statement	

This document is the property of Worldwide Clinical Trials Inc. and may not be duplicated, copied, altered or removed from company without prior approval from Worldwide Quality Assurance or in compliance with Worldwide Standard Operating Procedures.

Worldwide Clinical Trials Controlled Quality Management Document		
 WORLDWIDE CLINICAL TRIALS	Sponsor: Protocol Number:	Helixmith Co., Ltd. VMALS-002-2
STATISTICAL ANALYSIS PLAN VERSION 3.0		

year unless this partial start date is in same month as the first dose of study drug in which case the date of first dose of study drug will be used.

- If the stop date occurs before the start of study drug, the start date will be imputed as the first day of the month and year of the partial stop date.

If the start time is missing it will be imputed only in the case where the start date of the concomitant medication / event corresponds to the date of the first dose of study drug. The time will be imputed as the same time as the first dose of study drug. In all other cases the time will not be imputed.

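### The SAP's calendar-day TEAE rule contradicts the after-first-injection boundary in the same SAP section and in the protocol, so predose Day 0 procedure events could enter the primary TEAE incidence

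*SAP*

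**What the plan says.** The operative rule is in the TEAE definition of SAP 6.14.1: "AE will be considered as TEAE if it emerged or worsened on the day of first dosing or later to the end of study". It refers to a day and uses no clock time.

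Two other statements in SAP 6.14.1 use the dose as the boundary. The next bullet of the definition says an event is "considered a TEAE due to its appearance at or after the treatment has been administered". The opening paragraph says TEAEs and TESAEs "will be collected after first injections on Day 0 through Day 180/End of Treatment". A further sentence separates only Screening events: "Any AEs reported during Screening after completion of informed consent will be collected and recorded separately from TEAEs reported on Day 0". It does not say where a predose Day 0 event belongs.

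The protocol is time-based for TEAEs. Footnote 22 of the Schedule of Activities reads: "After the start of the 1st Injections on Day 0 through Day 180, AEs will be recorded as treatment-emergent adverse events (TEAEs"). The Synopsis (Overall Design) and Section 8.5.1 agree. For serious events, however, footnote 22 says: "Treatment-emergent serious adverse events (TESAEs) occurring after randomization and throughout the study will be recorded".

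On the Day 0 biopsy, the footnotes to the Schedule of Activities say: "It is collected predose on Day 0". Only the Day 84 biopsy is marked optional.

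SAP 6.2.5 foresees an AE start time. If the time is missing and the start date is the first-dose date: "The time will be imputed as the same time as the first dose of study drug". SAP section 9 declares no departure from the protocol's analysis.

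**The concern.** TEAE and TESAE incidence by arm is a primary endpoint (SAP 3.1). The calendar-day sentence is the only one in SAP 6.14.1 that a programmer can turn directly into a flag. On Day 0, after randomization and before any injection, participants have strength testing by HHD (and ATLIS where available), SVC and a gastrocnemius biopsy. Protocol 10.2.1 counts events associated with a study procedure as AEs. A bleed or leg pain from the biopsy that starts before the first injection is therefore pre-treatment under the protocol and a TEAE under the SAP's day rule.

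The gastrocnemius is also an injected muscle, so such an event would sit under preferred terms that injections can produce as well. Because the SAP treats an AE with missing relationship as drug-related, a predose event could also reach the table of related TEAEs (14.3.1.15). Two programmers reading the same section could produce different primary tables.

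**Working it through.** **Step 1. The boundaries side by side.**

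| Source | TEAE starts | TESAE starts |
|---|---|---|
| SAP 6.14.1, operative sentence | calendar day of first dosing | not stated |
| SAP 6.14.1, definition bullets on timing | at or after administration | at or after administration |
| SAP 6.14.1, opening paragraph | after first injections | after first injections |
| Protocol 8.5.1 | after first injections | after first injections |
| Protocol footnote 22 | after the first injections start | after randomization |

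The SAP's day rule is the outlier for TEAEs, and footnote 22 is the outlier for TESAEs. Footnote 22 also classes a procedure-related serious event before the first injections as an SAE. A serious biopsy complication after randomization but before injection is thus both a pre-treatment SAE and a TESAE within one footnote.

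**Step 2. Which events change class.**

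- Procedure-related, starts predose on Day 0, start time recorded: TEAE under the day rule, not under a dose-time rule.
- The same, start time missing: TEAE under both, because 6.2.5 imputes the dose time.
- Predose and unrelated to a study procedure: medical history, not an AE (Protocol 8.5.1, SAP 6.14.1). Protocol 8.2.2 is less clear on this.
- Starts or worsens after the first injection, or follows the Day 84 or Day 144 biopsy: TEAE under both.

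Only the first group is affected.

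**Step 3. Size.** The plan gives no figure for this point. The inputs from the protocol check out: 18 at 2:1 is 12:6 (Section 5.3), and 17/18 = 94.4% had an AE in the Phase 1/2 ALS study (Synopsis). The documents give no predose event rate *b*. It is assumed here, equal in both arms and independent of other TEAEs.

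- One participant whose only event of a given type is predose: 1/12 = 8.3 points (Engensis); 1/6 = 16.7 points (Placebo).
- Chance of at least one participant with a predose event, 1 − (1 − b)^n:

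| b (assumed) | Engensis, n = 12 | Placebo, n = 6 |
|---|---|---|
| 5% | 46% | 26% |
| 10% | 72% | 47% |
| 30% | 99% | 88% |

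- Rise in incidence over a background *g*: [1 − (1 − g)(1 − b)] − g = (1 − g)b. With g = 17/18, this is 0.10/18 = 0.6 points at b = 10% and 0.30/18 = 1.7 points at b = 30%. With an assumed g = 30% for one category, it is 0.7 × 10% = 7 points and 0.7 × 30% = 21 points.
- Effect on a risk difference, if misclassification is equal in both arms: it is multiplied by (1 − b). An assumed 50% versus 20% (30 points) becomes 27 points at b = 10% and 21 points at b = 30%.

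**The case against.** The strongest defence is that the SAP, read as a whole, does not intend to count predose events. The sentence before the day rule requires the event to be absent at pretreatment, the next bullet ties it to administration, and the time imputation in 6.2.5 fits a dose-time rule. This stands as far as intent goes. A reader might infer a settled decision to count every predose Day 0 event, and the documents do not support that. What they show is a contradiction, and it still needs removing because the day sentence is the one that can be programmed.

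A reader might also infer that the SAP's day rule governs TESAEs. The SAP's TESAE definition has no day-level sentence, so the rule reaches TESAEs only by reading a TESAE as a serious TEAE. The direct conflict on serious events is footnote 22. In addition, the Safety Analysis Population requires at least one Study Injection, so a participant never injected after a serious predose event would not appear in these tables.

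The consequences are limited. No formal safety testing is planned (Protocol 9.3.1). Randomization and blinding precede the biopsy, so misclassification should be non-differential. Tables by relationship separate events judged unrelated, and all AEs are listed. An inclusive rule also matches the SAP's other defaults for missing severity and relationship. These points lower the weight of the concern, but they do not settle which events belong in the primary table.

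**Conclusion.** The point holds as an internal contradiction in the SAP and an undeclared mismatch with the protocol, and it should be corrected before database lock. The exposure is confined to procedure-related events that start on Day 0 before the first injection. A correction will not take biopsy events out of TEAE incidence generally.

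One might multiply an assumed event rate by 18 and infer that several participants gain a spurious TEAE. That overstates the effect, because incidence changes only for participants with no other qualifying event. With a background near 94.4%, the rise of 0.6 to 1.7 points is about 0.1 to 0.3 of 18 participants (18 × 0.10/18 and 18 × 0.30/18). The larger effect is on low-count preferred terms, where one participant is 8.3 or 16.7 points. Nor is it safe to infer that serious events will be near zero, so that one misclassified event would be the whole result in an arm: the Phase 1/2 study reported SAEs in 3 of 18 participants.

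These sizes rest on an assumed predose event rate, independence from other TEAEs, equal rates in both arms, and the Phase 1/2 AE incidence as a stand-in for this trial's background.

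**What to change.** Replace the day-level sentence in SAP 6.14.1 with a date-and-time rule: an AE is treatment-emergent if its onset or worsening is at or after the start of the first Study Injection. If the start time is missing on the first-dose date, it is imputed under 6.2.5 and the event counts as a TEAE. State that a TESAE is a serious event meeting the same boundary. List predose Day 0 events separately, so that biopsy and strength-test events remain visible. Reconcile footnote 22 of the Schedule of Activities with Protocol 8.5.1 on when TESAEs start.

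The SAP part costs one sentence, one programming condition and one listing. Footnote 22 needs a change to the protocol. The rule also depends on AE start times being recorded on Day 0: the SAP says how to impute a missing time but does not show that times are routinely collected. Events without a time will stay classified as TEAEs, as they are now.
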